This study will investigate neuropsychological disease and treatments before and after severe COVID-19 disease. The two main aims are:

1. to evaluate the associations of pre-existing neuropsychological diseases and treatments with severe COVID-19 outcomes in comparison to patients without pre-existing neuropsychological pathology;

2. to evaluate the associations between hospital or ICU admission due to COVID-19 and neuropsychological sequelae following discharge home in comparison to patients with ICU admission due to non-COVID-19 severe acute respiratory infections (SARI).

Objectives

- 1. To assess whether pre-existing neuropsychological diseases (by separate diseases and overall) are associated with severe COVID-19 outcomes (hospital and ICU admission and death) in comparison to the general population.
- 2. To assess whether pre-existing neuropsychological treatments (as a class and individually where possible) are associated with severe COVID-19 outcomes (hospital and ICU admission and death) and whether these explain disease associations in comparison to those not receiving such treatments.
- 3. To assess whether the risk of severe COVID-19 outcomes with prior neuropsychological disease differs from the risk of severe outcomes with SARI.

After discharge following a hospital admission for COVID -19 infection:

- 4. To assess the incidence of new neuropsychological diseases up to one year after hospital and ICU discharge following treatment for COVID-19 disease.
- 5. To compare the incidence of new neuropsychological diseases up to one year after hospital and ICU discharge with COVID-19 disease to the incidence following discharge after treatment for SARI.

Summary of the potential impact

This study will provide a better understanding of how pre-existing psychopathology and concomitant medication affect the risk of hospital and ICU admission and death due to COVID-19 and how any differences between those with and without preexisting psychopathology and COVID-19 infection compare to other severe acute respiratory infections. We will discover the neuropsychological sequelae of admission to a hospital or ICU with COVID -19 disease, taking into account prior neuropsychological disease and whether these differ from patients discharged from an ICU following SARI. These findings will be key to prevention and management of ongoing problems for these patients.

METHODS

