A retrospective cohort data linkage study of patients aged 18 years and above registered in English general practices. This protocol is written following RECORD guidance [12].

Settings Describe the setting, locations, and relevant dates, including periods of recruitment, exposure, follow-up, and data collection.

1205 general practices in England contributing to the QResearch database, which is nationally representative. We defined cohorts during the COVID pandemic as between 24th January 2020 (the date of the first confirmed COVID-19 case in England) and study end (30th June 2021). We defined retrospective comparison cohorts as the 5 years prior to this date (24th January 2015- 23rd January 2020).

Data linkage

The study will include adult patients registered with the QResearch database. Practices must have been contributing to the QResearch database for at least 12 months. For the investigation of associations of pre-existing neuropsychological diseases and treatments (cohort 1) patients must be registered for at least a 12-month period before 24th January 2020. For the investigation of incidence of new neuropsychological diseases (cohort 2) patients must be registered for at least a 12-month period between January 2015 to 2020. The date of study entry is separately defined below for each study cohort.

Patients in QResearch will be linked to: (1) the ICNARC Case Mix Programme (CMP) database, the national clinical database from adult critical care; (2) the Hospital Episode Statistics (HES) data warehouse containing records of all patients admitted to NHS hospitals and Emergency departments in England; (3) the national registry of COVID-19 RT-PCR positive test results from Public Health England (PHE); and (4) Office of National Statistics COVID-19 mortality data, which includes all deaths due to COVID-19 in England. Data linkage will be based primarily on NHS number. For a description of the datasets see Supplemental material S1.

Participants

Give the eligibility criteria, and the sources and methods of selection of participants. Describe methods of follow-up. The methods of study population selection (such as codes or algorithms used to identify subjects) should be listed in detail.

Aim 1.

From the linked dataset, we will extract two cohorts to explore the association between neuropsychological diseases and treatments and hospitalisation, ICU admission or death:

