 Cohort one is adult patients aged 18 years of age or over on 24th January 2020 (the study entry date, when the first confirmed COVID-19 case occurred in the UK) who were registered in a primary care practice within the QResearch programme on or before 24th January 2019. Patients will be followed-up from study entry date until development of severe COVID-19 disease, defined as the first date of either hospitalisation, ICU admission, or death. Patients will be censored at the first occurrence of deregistration from the GP practise, death, or date of the final data extract from the linked datasets.

Cohort two is an open cohort of patients aged 18 years of age or over (including those who become 18 within this period) who had been registered with a primary care practise within the QResearch database for at least one year, between 24th January 2015 and 23rd January 2020. For each patient, the earliest day on which all these conditions were met will be defined as their study entry date, and they will be followed-up until development of severe disease due to SARI, defined as hospitalization, ICU admission, or death. Patients will be censored at the earliest of first occurrence of deregistration from the GP practise, death from other causes, 24th January 2020 or date of the final data extract from the linked datasets.

Aim 2.

- Cohort three will include adult patients (aged 18+ on date of hospital admission) discharged alive following a hospital admission including an ICU admission resulting from COVID -19 infection (defined below) between 24 January 2020 and study end date, who were registered in a primary care practice within the QResearch programme before their ICU admission. It will be used to evaluate the risk of subsequent neuropsychological sequalae from the date of discharge. Patients will be censored at the earliest of first occurrence of deregistration from the GP practice, death from other causes, 12 months post discharge from hospital, or date of the final data extract from the linked datasets.

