For cohort two, our primary outcome is the first occurrence of either hospital admission with SARI in the HES dataset (defined as a new ICD-10 code J09-J22 in the HES dataset) or ICU admission in the ICNARC CMP dataset with SARI (defined as any admission with unique diagnostic code any one of RE129 RE131 RE82 RE50 RE86 RE94 RE75 RE133 RE132 RE121 RE1 RE128 RE16 RE130 RE117 RE42 RE41) or death. Secondary outcomes will be each of these three events considered separately (I.e. SARI related hospital admission, ICU admission, death).

Aim 2.

Our primary outcome is development of new neuropsychological disease up to 1 year following hospital discharge which we define as having received a diagnostic code as below:

- Anxiety and stress-related disorders [ICD F40-48 and corresponding Read codes]
- Mood disorders [ICD F30-39 and corresponding Read codes]
- Psychotic disorders [ICD F20-29 and corresponding Read codes]
- Dementia [ICD F00-F03, G30, G31.0 ? and corresponding Read codes]

Secondary outcomes are the diagnosis of new neuropsychological disorders (as defined above) with treatment, and where numbers are available the new diagnosis with or without treatment of each class of disorders, each considered as a separate endpoint.

Neuropsychological treatments are defined as:

- Hypnotics and anxiolytics: (hypnotics, anxiolytics, barbiturates and methyprylone, benzodiazepines)
- Antidepressant drugs (Tricyclic and related antidepressant drugs, Monoamine-oxidase inhibitors, Selective serotonin re-uptake inhibitors, Other antidepressant drugs)
- Drugs used in psychoses and related disorders (Antipsychotic drugs and depot injections, Lithium salts, Phenothiazine derivatives)

Definition of exposures

Aim 1

Neuropsychological disease will be defined as an ordinal variable with the following three categories: no relevant diagnosis or drugs; diagnosis ever recorded without recent drug treatment; diagnosis present with recent drug treatment (with at least two prescriptions for neuropsychological treatments as above within the six months preceding study entry).

Our primary exposure is active neuropsychological disease on the study entry date which we define as having received a diagnostic code as above (24th January 2020 for cohort 1 and 24th January 2015 for cohort 2).

Aim 2.

The primary exposure is a hospital or ICU admission resulting from COVID-19 infection. Comparator exposures are hospital or ICU admission resulting from SARI.

Covariates

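### The fixed cohort 2 exposure date (24 January 2015) contradicts that cohort's individual entry dates, and in both Aim 1 cohorts patients with drugs but no coded diagnosis have no consistent exposure level

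*Protocol*

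**What the plan says.** **Entry dates (Protocol, Participants, Aim 1).** Cohort 1 has a single entry date, 24 January 2020. Cohort 2 is an open cohort running from 24 January 2015 to 23 January 2020. It admits people who reach 18 during that period and requires a year of registration. For each patient, "the earliest day on which all these conditions were met will be defined as their study entry date".

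**Exposure (Protocol, Definition of exposures, Aim 1).** Two definitions stand next to each other:

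- An ordinal variable with three levels: "no relevant diagnosis or drugs; diagnosis ever recorded without recent drug treatment; diagnosis present with recent drug treatment". Recent treatment means two or more relevant prescriptions in the six months before study entry.
- A primary exposure defined by a diagnostic code alone. It is read at study entry, and a bracket then gives that date as "24th January 2020 for cohort 1 and 24th January 2015 for cohort 2".

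**Use (Protocol, Objectives and Statistical Methods, Aim 1).** Objective 2 asks about treatments "in comparison to those not receiving such treatments". Objective 3 compares the risk associated with prior disease between COVID-19 and SARI, and cohort 2 is to be analysed with the same exposure variables as cohort 1. Statistical Methods also allows an optional time-varying indicator for a diagnosis or treatment that first appears after entry in patients who had neither at entry.

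**The concern.** The bracket and the rule that it explains cannot both hold for a patient who enters cohort 2 after 24 January 2015. If an analyst follows the bracket, a diagnosis made after that date but before the patient's own entry is not counted, although it is known at baseline. The patient then sits in the reference group. The prescription window is tied to study entry, so diagnosis and treatment would be read at different dates for the same person.

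Cohort 1 has one entry date and no such conflict. The error is therefore one-sided: it pulls the SARI hazard ratio towards 1 and leaves the COVID-19 hazard ratio alone. Objective 3 sets these two estimates side by side, so part of any apparent COVID-specific excess could come from the definition. The plan uses a database of about 8.3 million adults, so sampling error is likely to be small and an avoidable bias matters more than usual.

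The second problem is separate and affects both cohorts. A patient with relevant prescriptions but no coded diagnosis has no place among the three levels. Under the code-only definition the same patient is unexposed. Two analysts could build different variables from this text, and one of them would have treated people in the reference group.

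**Working it through.** The plan states no figure on this point, so there is nothing to reproduce. Three checks follow.

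**1. Gap between the fixed exposure date and entry in cohort 2**

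| Patient | Entry date | Gap from 24 January 2015 |
|---|---|---|
| Adult already registered for a year on 24 January 2015 | 24 January 2015 | 0 days |
| Adult who registers on 24 January 2015 | 24 January 2016 | 365 days |
| Adult who registers on 24 July 2017 | 24 July 2018 | 1277 days (3.5 years) |
| Registered patient who turns 18 on 23 January 2020 | 23 January 2020 | 1825 days (5.0 years) |

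The last patient would be classified from the record at age 13. The third would be classified at a date before registration.

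**2. Diagnosis by prescriptions in the prior six months, against the three levels**

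| Coded diagnosis | Prescriptions | Ordinal level | Code-only primary exposure |
|---|---|---|---|
| No | 0 | 1 | Unexposed |
| No | 1 | none | Unexposed |
| No | 2 or more | none | Unexposed |
| Yes | 0 | 2 | Exposed |
| Yes | 1 | 2 | Exposed |
| Yes | 2 or more | 3 | Exposed |

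Four of six cells are classified. If the word drugs in the first level is read as recent drugs under the two-prescription rule, the single-prescription cell moves to level 1. The cell with two or more prescriptions and no diagnosis still has no level.

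**3. Size of the date error: an illustration on assumed inputs**

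None of these inputs is in the documents:

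- diagnosed by 24 January 2015: p = 0.20
- new diagnoses among the undiagnosed: i = 0.02 to 0.04 per year
- mean gap for late entrants: g = 1.5 to 2.5 years
- late entrants as a share of cohort 2: s = 0.10 to 0.40

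Share of late entrants whose exposure is missed: m = (1 − p) × [1 − (1 − i)^g].

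- Low: 0.80 × (1 − 0.98^1.5) = 0.024
- High: 0.80 × (1 − 0.96^2.5) = 0.078

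Sensitivity of the exposure in late entrants, p / (p + m): 0.20/0.224 = 0.89 down to 0.20/0.278 = 0.72.

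The observed reference group has size 1 − p and contains the missed patients, so

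observed HR = HR / {[(1 − p − m) + m × HR] / (1 − p)}.

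For the whole cohort, replace m by s × m.

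| True HR | Late entrants | Whole cohort |
|---|---|---|
| 2.0 | 1.82 to 1.94 | 1.93 to 1.99 |
| 1.5 | 1.43 to 1.48 | 1.47 to 1.50 |

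Worked ends for HR 2.0: in late entrants, 2/(1 + 0.0776/0.80) = 1.82 and 2/(1 + 0.0239/0.80) = 1.94. In the whole cohort, 2/(1 + 0.4 × 0.0776/0.80) = 1.93 and 2/(1 + 0.1 × 0.0239/0.80) = 1.99.

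The calculation gives missed patients the same hazard ratio as other exposed patients and weights by patients, not person-time.

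**Does anything else in the Protocol repair this?** The time-varying indicator is optional, starts after entry, and applies only to patients with neither diagnosis nor treatment at entry. It captures neither a diagnosis made between January 2015 and a later entry nor treatment without a diagnosis at entry.

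**The case against.** The best defence of the date is that the governing words are right. The sentence ties exposure to study entry, Participants defines that date individually, and the bracket may be only a loose reference to the start of the cohort. An analyst who follows the main clause makes no error. That is a fair reading, but the bracket is an explicit date inside the primary exposure definition, and the text does not say which prevails. It is a stated contradiction, not a detail left to an analysis plan.

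Several stronger readings are tempting and should not be drawn.

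- *All of cohort 2, or the Aim 1 exposure as a whole, is misclassified by date.* On the natural reading, adults with a year's registration on 24 January 2015 enter that day and are classified correctly, and the cohort 1 date agrees with its entry date. The Data linkage section could be read as requiring the year of registration to fall inside the window ("patients must be registered for at least a 12-month period between January 2015 to 2020"), which would make every entry late. However, that sentence describes its cohort 2 as the one for new disease, which does not match cohort 2 in Participants, so I do not rely on it.
- *The bias is large.* The figures near 1.8 apply to late entrants only and rest on assumed inputs. Objective 3 uses the whole cohort, where the shift is small.
- *Drug-only patients are dropped, or Objective 2 cannot be answered.* Nothing says they are excluded. Statistical Methods separately plans hazard ratios for individual treatments, and levels 2 and 3 already contrast treated with untreated diagnosed patients.
- *The missing level biases Objective 3 in the same one-sided way.* The gap is in the definition for both cohorts alike.
- *The ordinal variable will be fitted as a linear score.* The Protocol calls it ordinal but specifies no score.

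It can also be said that the coding of levels belongs in an analysis plan that is not shown. That would excuse silence. Here the document gives two definitions that treat the same patient differently.

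**Conclusion.** The concern holds in two limited parts.

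First, the cohort 2 exposure date contradicts the individual entry dates. Taken literally, it misclassifies some exposed late entrants as unexposed, in cohort 2 only, and attenuates the SARI hazard ratio relative to the COVID-19 one. On the assumptions above, a true hazard ratio of 2.0 falls by 0.3% to 3.8% in the whole cohort (0.006/2 to 0.075/2). The bias is modest and its exact size is unknown, because the documents give neither the share of late entrants nor the rate of new diagnoses.

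Second, in both cohorts, patients with relevant prescriptions and no coded diagnosis are unclassified by the ordinal variable and unexposed under the code-only variable. Where the code-only reference group serves as the comparator, it includes people who are receiving the treatments that Objective 2 studies. No size can be put on this from the documents.

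The case for correction rests less on the size of the bias than on the fact that the main Aim 1 exposure cannot be built uniquely from the text.

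**What to change.** Four changes in Definition of exposures, Aim 1:

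1. Replace the bracket with: *24 January 2020 for cohort 1; each patient's own study entry date for cohort 2*.
2. Anchor both the diagnosis and the prescription window to that date.
3. Add a separate level, *recent drug treatment without a recorded diagnosis*, so that these patients stay out of the reference group with neither. Because recent treatment needs two prescriptions, also say where a single prescription without a diagnosis belongs.
4. State which of the two definitions, the ordinal variable or the code-only variable, is primary, and use it in both cohorts.

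The cost is a few wording changes and one extra model parameter. No new data are needed.

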The following variables of interest were chosen as either due to known association with risk of developing severe COVID-19 and/or known associations with neuropsychological disease. Distributions of each variable will be summarised by cohort using descriptive statistics.

Demographics (Aims 1 & 2)

- Age
- Gender
- Material deprivation by quintile of Townsend deprivation score

- Ethnicity (White, Indian, Pakistani, Bangladeshi, other Asian, Black African, Chinese, and other ethnic group),
- Geographical region
- Domicile (homeless, care home residence, neither)
- Household size

Lifestyle (Aims 1 & 2)

- Body mass index (BMI)
- Smoking status (non-smoker, ex-smoker, light smoker: 1–9 cigarettes/day, moderate smoker: 10–19 cigarettes/day, heavy smoker: ≥20 cigarettes/day, not recorded)
- Alcohol intake (none, trivial: <1 unit/day, light: 1–2 units/day, medium: 3–6 units/day, heavy: 7–9 units/day, very heavy: >9 units/day, not recorded).

Co-morbidities (Aims 1 & 2)

- Cardiovascular diseases coronary heart disease, stroke/transient ischaemic attack, atrial fibrillation, congestive cardiac failure, thromboembolism, peripheral vascular disease, congenital heart disease, hypertension
- Respiratory diseases asthma, chronic obstructive pulmonary disease, rare lung conditions (bronchiectasis, cystic fibrosis, alveolitis), pulmonary hypertension or pulmonary fibrosis
- Endocrine diseases type 1 and 2 diabetes, hypothyroidism
- Chronic kidney disease
- Neurological conditions- epilepsy/seizures, Parkinson's disease, motor neurone disease, multiple sclerosis, myasthenia gravis, Huntington's disease
- Cancer blood cancer, respiratory tract cancer, and other relevant cancer
- Bone and joint conditions- osteoarthritis, rheumatoid arthritis or Systemic Lupus Erythematosis (SLE), osteoporosis, osteoporotic fracture (hip, spine wrist, humerus)
- Gastrointestinal diseases liver disease, liver cirrhosis
- Transplants solid organ transplant (excluding kidney and bone marrow), bone marrow or stem cell transplant
- Sickle cell disease or severe immunodeficiency
- Traumatic brain injury
- Learning disability/Down's syndrome, cerebral palsy

Medications/treatments (Aims 1 & 2)

- antihypertensive drugs,
- aspirin,
- statins,
- Anticoagulants,
- non-steroidal anti-inflammatory drugs,
- bisphosphonates,
- oral contraceptives,
- hormone replacement therapy,

- anticonvulsants
- chemotherapy
- radiotherapy
- immunosuppressant medication
- leukotriene or long-acting beta-agonist

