- oral steroids

Intensive care stay (Aim 2)

- Length of stay
- Duration of advanced respiratory support (invasive ventilation)
- Use of sedation in the first 24 hours of admission

Effect Modifiers

For aim 1, we assessed these potential confounders by creating directed acyclic graphs (DAG) to determine which variables were likely to be to some extent caused by the presence of prior neuropsychological disorders (as the exposure of interest), and which were not likely to be caused by the presence of prior neuropsychological disorders, but were thought to be independently potential predictors of severe Covid outcomes.

Variables from the above list to be included in the model are all those grouped under: demographics; co-morbidities; lifestyle factors; plus prescription of any immunosuppressants and/or anticoagulants. Other medications (as these are not believed to affect the risk of severe Covid outcomes), and in-hospital factors (length of stay and use of sedation during intensive care admission, as these are outcomes potentially caused by Covid severity) will not be adjusted for.

For aim 2, our exposure of interest is admission to intensive care with SARI (compared to admission to intensive care with SARI. This exposure occurs at a fixed time which is used as the baseline for our time to event analysis in predicting the outcome of interest, and all other variables listed above are measured before this baseline. Therefore (depending on the available sample size and number of events), all the previously listed covariates of interest may be included in our adjusted models.

Data sources

Intensive Care Unit admission data will come from the ICNARC CMP dataset Hospital admission and mortality will come from the HES dataset

All exposures and confounders and neuropsychological outcomes will come from the QResearch database.

COVID-19 infection test status will come from the national registry of COVID-19 RT-PCR positive test results from Public Health England (PHE).

Bias

To limit the possible impact of COVID-19 testing bias (collider bias) we will analyse the entire QResearch eligible population, rather than restricting analysis to only those with a positive COVID-19 test.

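### The Aim 1 DAG was drawn to identify variables caused by the exposure, but no variable is left out of the adjustment set on that ground, and only one set is named

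*Protocol*

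**What the plan says.** In Effect Modifiers, the protocol describes the purpose of the Aim 1 DAG as being "to determine which variables were likely to be to some extent caused by the presence of prior neuropsychological disorders (as the exposure of interest"). It contrasts these with variables unlikely to be caused by the exposure that "were thought to be independently potential predictors of severe Covid outcomes".

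The next paragraph fixes the adjustment set as every variable under "demographics; co-morbidities; lifestyle factors; plus prescription of any immunosuppressants and/or anticoagulants". Two groups are left out, each with a reason:

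- "Other medications (as these are not believed to affect the risk of severe Covid outcomes");
- length of stay and sedation in intensive care, "as these are outcomes potentially caused by Covid severity) will not be adjusted for".

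Under Covariates, the demographic group includes household size and "Domicile (homeless, care home residence, neither"). The lifestyle group holds "Body mass index (BMI"), smoking and alcohol.

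Definition of exposures counts a diagnosis recorded at any time before entry, with or without recent drug treatment. Statistical Methods (Aim 1) states one adjustment, for the covariates as listed, and applies the same methods to the secondary exposures and to cohort 2.

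**The concern.** The usual reason for asking which variables are caused by the exposure is to decide whether to condition on them. Here the question is put and then has no visible effect on the model.

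Objective 1 asks whether the diseases are associated with severe outcomes, and the Hypothesis section words this as disease raising the risk. A hazard ratio that holds care-home residence, household size, BMI, smoking, alcohol and all comorbidities fixed answers a narrower question: what is left once those routes are closed. Objective 2 asks whether treatments explain the disease associations, so it also needs a clear starting association.

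The Bias section sharpens the point. It expects the conditions to change exposure to COVID-19, in either direction, and adds a condition-specific secondary analysis to examine this. Domicile and household size are plausible routes for such a difference. Because that analysis uses the same methods, it can partly condition away what it was added to show.

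**Working it through.** **Text check.** The plan gives no figure on this point, so there is nothing to reproduce. Set side by side:

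| Item | What the protocol gives |
|---|---|
| Purpose of the DAG | Separate consequences of the exposure from independent predictors |
| Variables admitted | All demographics, lifestyle and comorbidities; immunosuppressants and/or anticoagulants |
| Reason for omitting other medications | No believed effect on outcome |
| Reason for omitting in-hospital factors | Possibly caused by COVID-19 severity |
| Variables omitted because the exposure causes them | None stated |
| Second adjustment set for Aim 1 | None named |
| Class given to each variable by the DAG | Not in the text; Figure 3 is not reproduced in the copy at hand |

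The exposure can predate covariate values held at study entry by years, so the time order allows those values to be its consequences.

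**Illustration of size.** All inputs are assumed. For a rare outcome and one binary mediator with hazard ratio h, present in a share p1 of exposed and p0 of unexposed patients (both conditional on the other covariates):

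total HR = direct HR × [1 + p1(h − 1)] / [1 + p0(h − 1)]

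The share of the log HR removed by adjusting for the mediator is [ln(total) − ln(direct)] / ln(total). With a direct HR of 1.30:

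| p0 | p1 | h | Total HR | Share of log HR removed |
|---|---|---|---|---|
| 1% | 3% | 1.5 | 1.30 × 1.015/1.005 = 1.31 | 4% |
| 20% | 30% | 2.0 | 1.30 × 1.30/1.20 = 1.41 | 23% |
| 1% | 10% | 4.0 | 1.30 × 1.30/1.03 = 1.64 | 47% |
| 20% | 40% | 4.0 | 1.30 × 2.20/1.60 = 1.79 | 55% |
| 1% | 3% | 0.8 | 1.30 × 0.994/0.998 = 1.29 | −2% |
| 20% | 40% | 0.8 | 1.30 × 0.92/0.96 = 1.25 | −19% |

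In the last two rows the mediator lowers risk, so adjusting for it raises the hazard ratio.

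**Simulation.** One run of 2,000,000 patients had a confounder C (30%), an exposure X with probability 0.15 + 0.10C, and a variable M with probability 0.10 + 0.10C + 0.10X. The event rate was 0.005, multiplied by 1.3 for X, 2 for M and 1.5 for C. The estimated rate ratios for X were:

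- unadjusted: 1.48;
- adjusted for C only (total effect): 1.38;
- adjusted for C and M: 1.27.

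The step from C only to C and M is 1.375/1.269 = 1.08. The formula gives 1.20/1.10 = 1.09 when C is absent and 1.30/1.20 = 1.08 when it is present. The move from 1.48 to 1.38 shows the other side: omitting a true confounder also distorts the estimate.

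**The case against.** Much of the opposing case stands.

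- **The DAG's result is not shown.** A reader might infer that the DAG flagged care-home residence, BMI, smoking, alcohol and comorbidities, and that the plan then adjusts for everything flagged. The text gives the purpose of the DAG, not its output, and the figure's absence from this copy is no error in the plan. Flagged variables could even be among the omitted medications. What can be checked is narrower: no stated omission rests on being caused by the exposure.
- **Several hazard ratios are planned.** A reader might infer that Aim 1 rests on one estimate. It does not: there are hazard ratios for the composite, for each component outcome, by disease, by treatment and for cohort 2. What is single is the adjustment set.
- **Removal of effect is not established.** The protocol calls these variables potential confounders, and many may be. Where they are, adjustment removes bias. Even for mediators, the sign depends on whether they raise or lower risk.
- **Full adjustment has a rationale.** The Introduction warns of residual confounding in earlier drug-class findings, and the objectives speak of association without naming a total effect.
- **A reduced model can be built badly.** Down's syndrome, congenital heart disease and sickle cell disease cannot be consequences of a later anxiety, mood, psychotic or dementia diagnosis. Dropping all comorbidities would open confounding rather than recover a total effect.

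It can also be said that extra columns of results belong in a statistical analysis plan. That would dispose of a mere omission. Here, though, the protocol itself fixes the set, directly after describing a distinction that the set does not use.

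**Conclusion.** The concern holds in a limited form. The stated purpose of the Aim 1 DAG and the adjustment set do not fit together, and plausible consequences of the exposure are conditioned on in the only set named. If they are mediators, the Aim 1 hazard ratios lie nearer to a direct than a total effect.

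The documents do not support a stated size or direction. The range of 4% to 55% of the log hazard ratio removed, or 2% to 19% added for a risk-lowering mediator, rests wholly on assumed prevalences, assumed mediator effects and a direct hazard ratio of 1.30. With about 8.3 million adults (Study Size), the issue is which quantity is reported, not its precision. The full model is defensible and should stay. This is a cheap improvement to interpretation and does not invalidate the analysis.

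**What to change.** 1. List in Effect Modifiers which variables the DAG classed as caused by prior neuropsychological disorder.
2. Keep the full model as it stands. Beside it, for each Aim 1 exposure in cohorts 1 and 2, report a pre-specified model that omits those variables. Retain age (spline), sex, ethnicity, region, deprivation, and comorbidities that are congenital or otherwise not caused by the exposure. Deprivation may itself be partly a consequence of illness, so say that keeping it is a judgement.
3. State that the full model conditions on possible mediators, and interpret objective 1 from both models. Do the same for the condition-specific analysis promised in the Bias section.
4. Align Statistical Methods (Aim 1) with Effect Modifiers. The former adjusts for the covariates as listed, and that list includes medications, such as statins and aspirin, which the latter leaves out.

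The cost is one extra model per exposure and one further column in the tables, from data already held. The reduced model may leave more confounding, which is why the full model stays beside it.
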